## 10 STATISTICAL CONSIDERATIONS

### 10.1 STATISTICAL HYPOTHESES

Primary Endpoint: We hypothesize that at least 60% of eligible patients approached will enroll in the mPal intervention.

### 10.2 SAMPLE SIZE DETERMINATION

The sample size of 80 patients is based on the goal of estimating the probabilities and means for 2 feasibility outcome measures (enrollment  $\geq 60\%$  [primary],  retention  $\geq 60\%$ ). We will use feasibility outcomes to inform a future trial. For structured interviews, we anticipate we will be able to identify key themes with 20 interviews.

### 10.3 POPULATIONS FOR ANALYSES

The patient sample ( $n = 40$  mPal;  $n = 40$  usual care) will be used to analyze feasibility and acceptability data and describe pre-post changes in patient-reported outcomes. The provider sample ( $n = 6$ ) will be used to demonstrate feasibility of measurement collection.

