#### Primary Objectives

1. Evaluate mPal’s feasibility and acceptability. We hypothesize we will be able to enroll  $\geq 60\%$  of asLC patients we approach (primary feasibility outcome), retain  $\geq 60\%$  for one-month follow-up, and achieve mean patient and provider feasibility ratings of  $\geq 3.5/5$ . For acceptability, we hypothesize we will be able to achieve mean patient and provider acceptability ratings of  $\geq 3.5/5$ . We anticipate qualitative data (n = 40 mPal patient interviews; n = 6 provider interviews) will further support the ease of use and clinical value of mPal.
2. Obtain preliminary data on effectiveness and equity outcomes for a planned trial. In line with best practices for pilot studies, we are not testing formal hypotheses for effectiveness outcomes; however, we will measure patient and provider PC knowledge and motivation and PC referrals, which we expect will improve with mPal. For equity outcomes, we will explore whether mPal appears similarly effective for patients with different characteristics (e.g., rural vs. urban, health literacy, income, race) by analyzing survey and semi-structured intervention data from mPal patients (n = 40).

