**Interviews.** Patients assigned to mPal (n = 20-40) will complete two interviews. The interviews will last approximately 10-15 minutes and will query overall satisfaction with the intervention, perceived impact of mPal on clinical care, and reasons patients chose or chose not to talk with their doctor about their palliative care needs. The interviews will take place over the phone, Zoom, or in-person, according to patient preference. Interviews will be conducted by the study team and audiorecorded. After each interview, the interviewer will write up observations in the form of field notes, which will include information about the setting (e.g., details about room if in-person vs. on the phone), personal environment (e.g., respondent's attitude and openness), social environment (e.g., presence of caregiver or others in room), and summary of patient's responses. Recordings will be transcribed verbatim, the transcripts checked for accuracy and deidentified.

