#### 10.4.2 ANALYSIS OF THE PRIMARY ENDPOINT(S)

The primary outcome of the feasibility is enrollment ( $\geq 60\%$ ). A one-sample binomial test will be used to compare the observed enrollment percentage to 60%.

Enrollment (primary): Number of patients enrolled divided by the number of eligible patients approached

Retention: The percentage of patients and providers who complete baseline and follow-up questionnaires.

Acceptability: Mean post-treatment patient and provider ratings  $\geq 3.5/5$  on intervention acceptability, feasibility, and appropriateness (psychometrically validated measure; Table 2), and a brief semi-structured interview to explore factors associated with acceptability.

---

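### The pre-post comparison is described on 40 per arm, but the t-tests on change use only patients with both T0 and T2: 24 per arm at the 60% retention floor, with no rule for missing follow-up

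*Combined protocol and SAP*

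**What the plan says.** Section 10.3 of the combined protocol and SAP names one patient set, 40 mPal and 40 usual care, which "will be used to analyze feasibility and acceptability data and describe pre-post changes in patient-reported outcomes". It does not separate randomised patients from those with follow-up data.

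Section 10.4.3 tests by t-test whether pre-post change differs between arms, and names PC knowledge and motivation as the effectiveness outcomes. It gives estimation of standard deviations for later studies as the main aim. Table 2 schedules both measures at T0 and T2 for all patients, and at T1 for mPal patients only.

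On retention, the synopsis objective is to "retain $\geq 60\%$ for one-month follow-up". Section 10.4.2 defines retention as "The percentage of patients and providers who complete baseline and follow-up questionnaires". Section 10.2 repeats the 60% and states: "The sample size of 80 patients is based on the goal of estimating the probabilities and means for 2 feasibility outcome measures". Section 8.2 allows replacement of consented patients who do not receive the intervention, but not of those who withdraw after receiving it. Section 10.4.1 compares dropouts by demographic and clinical characteristics. No section gives a rule for missing T2 data.

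The mPal-only counts vary. The synopsis gives 40 interviews, and for equity it proposes to proceed "by analyzing survey and semi-structured intervention data from mPal patients (n = 40"). Section 3 gives 30-40 for both, and Section 4.1 gives 30-40 interviews. Section 9.1 says: "Patients assigned to mPal (n = 20-40) will complete two interviews". Section 10.2 regards 20 interviews as enough to identify themes.

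**The concern.** A between-arm comparison of change needs a T2 value. Under Table 2 the usual care arm has no other post-baseline measure of knowledge or motivation, so a usual care patient lost before T2 leaves the analysis. The plan would count 60% retention as success, yet the only number attached to the pre-post analysis is the full 40 per arm.

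Two things are at stake. The first is precision: the standard deviations and arm differences meant to inform the next trial may rest on far fewer patients than 10.3 suggests. The second is bias. In an unblinded trial where one arm receives palliative care education, the patients who stay to T2 may differ between arms in baseline knowledge or attitude. A t-test on completers' change scores does not correct for that.

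**Working it through.** **Inputs.** 40 per arm (10.3); retention of at least 60% (synopsis, Section 3, 10.2); change scores compared by t-test (10.4.3); T0 and T2 as the only time points common to both arms (Table 2). I assume equal retention in the two arms and that the one-month follow-up in the retention objective is T2. Table 2 supports the latter, since it places the one-month post-mPal referral survey at T2.

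**1. The plan's own figure.** 40 + 40 = 80, which agrees with 10.2. The plan states no effect size, SD, power, target CI width or dropout allowance, so nothing further can be reproduced.

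**2. Patients with paired data.** Number per arm = 40 x retention.
- 60%: 24 (48 in total)
- 75%: 30
- 80%: 32
- 90%: 36
- 100%: 40

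**3. Precision of the arm difference in change**, in units of the SD of change. Half-width = t(0.975, 2n - 2) x sqrt(2/n).
- n = 40: 1.991 x 0.2236 = 0.445
- n = 24: 2.013 x 0.2887 = 0.581

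For the SD in one arm, the 95% CI is the estimate times sqrt((n - 1)/chi-square quantile).
- n = 40: 0.82 to 1.28 times the estimate
- n = 24: 0.78 to 1.40 times the estimate

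**4. Bias of the completer t-test.** Suppose there is no true effect, the scores have equal SD at T0 and T2 with correlation r, and dropout depends only on the baseline score. Among completers, expected change is -(1 - r) x (their mean baseline minus the overall mean). Randomisation makes the overall mean the same in both arms, so

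bias = -(1 - r) x D,

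where D is the difference between arms in completers' mean baseline, in SD units. Neither r nor D is given in the plan. For illustration, with r = 0.5:
- D = 0.20 gives a bias of 0.5 x 0.20 = 0.10 SD in absolute size
- D = 0.48 gives 0.5 x 0.48 = 0.24 SD in absolute size
- D = 0 gives none

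Simulation with about 60% retention and baseline-dependent dropout differing by arm gave 0.10 to 0.24 SD for the completer t-test. A baseline-adjusted analysis was unbiased and had a smaller standard error. The standard error follows from the residual SDs: sqrt(2(1 - r)) for change scores and sqrt(1 - r^2) after adjustment. At r = 0.5 these are 1.00 and 0.87.

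**5. Interview counts.** Of 40 mPal patients, 30 is 30/40 = 75% and 20 is 20/40 = 50%. If each has a 60% chance of reaching T2, the chance that at least 30 do is 3.5%, and that at least 20 do is 93%. For a T2 interview, the range in Section 9.1 is therefore compatible with the retention floor. The range in Sections 3 and 4.1 is unlikely to be met at that floor, and the synopsis figure of 40 allows no loss.

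**The case against.** The strongest reply is that 10.3 simply names the randomised sample and that 60% is a threshold for success, not a forecast. Early losses may be replaced, and under Section 8.1 patients who stop the intervention still complete assessments. All of this stands. It makes 24 the lowest equal-arm result that meets the criterion, not the expected number. It does not say who enters the change-score analysis or what happens when T2 is missing.

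A reader might infer more than the documents support:
- **That equity and interviews also assume 40 per arm and full retention.** Both are mPal only, and only the synopsis gives 40. One of the two interviews is at T1 (Section 5.6). Referrals come from the EHR, and mPal patients have a T1 knowledge score, so equity does not require T2 completion. Twenty-four interviews would satisfy both 9.1 and 10.2.
- **That 10.3 gives the wrong denominator for the primary endpoint.** Section 10.4.2 already defines enrollment as "Number of patients enrolled divided by the number of eligible patients approached". Feasibility in 10.3 can fairly mean ratings and retention, which do come from enrolled patients.
- **That the trial misses a promised power.** None is stated for these outcomes, and the objectives disclaim formal effectiveness hypotheses. The size of 80 rests on feasibility estimates.

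It can also be said that a model cannot recover absent T2 values. That is right: patients with a baseline only add little information on change and do not restore 40 per arm. The gain is protection against baseline-related dropout and a smaller residual variance. The dropout comparison in 10.4.1 may reveal such dropout but does not correct for it.

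**Conclusion.** The point holds for the pre-post comparison in 10.3 and 10.4.3. The 40 per arm is a randomised number. The analysis as written uses 24 to 40 per arm over 60% to 100% retention. At the floor the CI half-width for the arm difference is about 0.58 SD instead of 0.45 SD, and the upper confidence factor for a one-arm SD is 1.40 instead of 1.28.

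The completer t-test is biased if dropout depends on baseline and does so differently by arm. The 0.10 to 0.24 SD is conditional on assumed dropout patterns; the plan gives no data on how likely they are. If dropout is unrelated to baseline, or acts alike in both arms, this bias vanishes and only the loss of precision remains.

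The interview and equity counts are a separate inconsistency of wording. The primary endpoint, the sample size and the feasibility decision do not change. This should be corrected, but it does not threaten the trial's main purpose.

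**What to change.** 1. **Section 10.4.3.** For PC knowledge and motivation, replace the change-score t-tests with a baseline-adjusted repeated-measures model on T0 and T2 that includes every randomised patient with a baseline. Keep T0 in the outcome vector with a common baseline mean across arms. If baseline enters only as a covariate, patients without T2 drop out again. Report the arm difference with its 95% CI and the number contributing at T2 in each arm.
2. **Section 10.3.** State that 40 per arm is the number randomised, and that paired T0/T2 data are expected for 24 to 40 per arm at 60% to 100% retention.
3. **Synopsis and Sections 3, 4.1 and 9.1.** Give one mPal-only interview count, by time point if T1 and T2 differ, and one equity count. Do not restrict equity to T2 completers, because EHR referrals and T1 knowledge scores remain usable.

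The cost is rewording and slightly more analysis work. No extra patients or data are needed. The model assumes that T2 data are missing at random given arm and baseline. The plan should say so, because dropout driven by unobserved T2 status would bias this analysis too.

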### 10.4 STATISTICAL ANALYSES

#### 10.4.1 GENERAL APPROACH

We will use descriptive statistics (means, standard deviations, median, range) to examine the distribution of continuous variables. We will calculate 95% CIs for each of the feasibility measures to determine the range of estimates that are consistent with our data.

We will use one-sample negative binomial probabilities and tests of binomial proportions to compare to hypothesized values. We will summarize reasons for ineligibility and refusal and compare patients who drop out or do not adhere by demographic and clinical characteristics. Ordinal scaled variables such as feasibility and acceptability will be compared between groups

before and after baseline (as well as change from baseline) using the Wilcoxon Rank Sum statistic. Within group comparison of the pre versus post baseline measures will be evaluated using the Wilcoxon Signed Rank statistic.

We will use qualitative methods to analyze patient and provider feedback from the exit interviews and descriptive statistics to summarize participants' acceptability, feasibility, and appropriateness ratings of the intervention. The interviews will be transcribed verbatim and managed in ATLAS.ti or other qualitative software for analysis. The PI and study coordinator will code interviews by domains (e.g., perceived impact of mPal on clinical care, barriers, facilitators to using mPal, suggested changes to improve equity of mPal). Data will be analyzed using thematic content analysis to describe perceptions.

Statistical significance will be indicated by  $p < .05$ .

---

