**Table 2. Aim 1 and 2 Measures**

Construct	Description	Data Sources	Level		Schedule
			Pt	Pv/Sy	
Aim 1. Implementation Outcomes					
Feasibility	FIM  : 4 item implementation measure of intervention feasibility ( $\alpha = .89$ ); Individual interviews (pts, pvs)	Survey; interviews	X	X	mPal Patients: T1 Providers: T3
Acceptability	AIM  : 4 item implementation measure of intervention acceptability ( $\alpha = .85$ ) individual interviews (pts, pvs)	Survey; interviews	X	X	mPal Patients: T1 Providers: T3
Aim 2. Effectiveness and Equity Outcomes related to Planned Future Trial					
PC referral	Proportion of patients in each arm who receive a referral to PC within 1-month (survey) and 3-months (EHR) post-mPal intervention	EHR, Survey	X	X	Patients: T2 (survey); System: 3-months post intervention (EHR)
PC knowledge	HINTS PC  : 10 items; assesses self-reported PC knowledge and PC perceptions. PACKS	Survey	X	X	Patients: T0, T1 (mPal only), T2 Providers: T0, T1, T3
Motivation to use PC	PCAS-9  : 9 items; assesses emotional, cognitive, and behavioral components of motivation to use PC ( $\alpha$ 's = .70-.90)	Survey	X	X	Patients: T0, T1 (mPal only), T2 Providers: T0, T1, T3
Opportunities to use PC	5 items; perceived ability to access PC. Based on preliminary study and literature. 	Survey,	X	X	Patients: T0, T2 Providers: T0, T3
PC discussion	2 survey items; Interview questions to supplement (experiences discussing PC during clinical encounters, quality of discussion, how mPal was used)	Survey, depth interviews	X	X	Patients: T0, T2 Providers: T0, T3
Demographics	15 items; sociodemographics, health literacy  (pts), PC training (providers)	Survey	X	X	Patients: T0 Providers: T0
Equity	Characteristics of mPal patients who do/do not seek PC referral and do/do not show knowledge increase; Interview with those who do/do not use PC; barriers	Survey, interviews	X	X	mPal Patients: T2, 3m post intervention

Note. Pt = Patient; PV = provider; Sy = System; T = timepoint; T0 = baseline; T1 = post mPal app viewing or knowledge check (pt assessment); post webinar viewing (providers); T2 = 8-week follow-up (pt assessment); T3 = post-patient-level intervention period (for providers)

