#### 10.4.3 ANALYSIS OF THE SECONDARY ENDPOINT(S)

We will describe pre-post changes in the patient-reported outcome variables related to a future trial using univariate and bivariate statistics. Our chief goals will be to estimate the standard deviations of our key variables for use in planning future studies. We will examine, through the use of t-tests, whether pre-post changes in the mPal differ significantly from pre-post changes in the control group. If our intervention is successful, we would expect to see significantly greater improvement over time in our effectiveness outcomes (PC knowledge, motivation) in treatment vs. control. We will also examine correlations between changes in these measures and PC referrals; we expect changes in PC knowledge and motivation variables will be positively correlated with changes in PC referrals within both treatment and control groups.

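### Section 10.4.1 names feasibility and acceptability for rank tests that their single measurement in Table 2 cannot support, and Section 10.4.3 uses change-score t-tests where adjusting T2 for T0 would usually be more precise at no data cost

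*Combined protocol and SAP*

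**What the plan says.** **Rank tests.** Section 10.4.1 plans: "Ordinal scaled variables such as feasibility and acceptability will be compared between groups". The same sentence sets the time points and the test for that comparison: "before and after baseline (as well as change from baseline) using the Wilcoxon Rank Sum statistic". Its next sentence adds a within-group signed-rank test of pre against post values.

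**When the ratings are taken.** In Table 2 (Section 9.1) the Feasibility (FIM) and Acceptability (AIM) rows carry the same schedule: "mPal Patients: T1 Providers: T3".

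**Other text on the ratings.** Section 10.4.1 also promises 95% CIs for the feasibility measures and descriptive summaries of acceptability, feasibility and appropriateness. Section 10.4.2 sets a target mean of at least 3.5 out of 5 "on intervention acceptability, feasibility, and appropriateness (psychometrically validated measure; Table 2").

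**Knowledge and motivation.** Section 10.4.3 states: "We will examine, through the use of t-tests, whether pre-post changes in the mPal differ significantly from pre-post changes in the control group". No baseline covariate is named. Table 2 schedules both constructs as "Patients: T0, T1 (mPal only), T2", so T0 and T2 exist in both arms. Under Section 6.3, allocation stays unknown to staff and patients until the baseline questionnaire is complete.

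**The concern.** There are two separate matters.

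(a) The two variables that 10.4.1 offers as examples for the rank tests are two that have no comparison data. Both scales rate the intervention itself, so a usual-care or pre-exposure value would have little meaning even if it were collected. An analyst following the text would have to abandon these tests or improvise, for ratings that serve the first primary objective. The pointer from 10.4.2 to Table 2 for appropriateness leads nowhere, because Table 2 gives neither an instrument nor a time point for it.

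(b) A change score fixes the coefficient of T0 at 1. When the true regression slope of T2 on T0 is below 1, this over-corrects and adds noise. The between-arm estimate for knowledge and motivation is then wider than the collected data allow, in a pilot meant to inform a larger trial.

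**Working it through.** **(a) Tests against data.** The documents give no figure to reproduce here.

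| What 10.4.1 requires for FIM and AIM | What Table 2 supplies |
|---|---|
| Between groups, before baseline | No T0 rating in either arm |
| Between groups, after baseline | mPal patients only; no usual-care rating |
| Between groups, change from baseline | No T0 rating, no usual-care rating |
| Within group, pre against post | Post only |

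The only two sets of people with ratings are mPal patients (T1) and providers (T3). That is not an arm comparison, and it yields no change score.

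A one-group mean with a CI can be supported. Half-width = t(0.975, n-1) × SD / √n.
- 40 mPal patients: 2.023 / √40 = 0.32 SD.
- 6 providers: 2.571 / √6 = 1.05 SD.

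For an assumed SD of 0.6 to 1.0 points, these are 0.19 to 0.32 points (patients) and 0.63 to 1.05 points (providers).

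**(b) Change score against baseline adjustment.** Section 10.2 gives 80 patients but no SD, correlation, effect size or target width for these outcomes, so again there is no figure to reproduce.

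Inputs: 40 per arm (Section 10.3). Assumed: T0-T2 correlation ρ of 0.3, 0.5 and 0.7, and SD ratio k = SD(T2)/SD(T0), first set to 1.

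- Change-score variance per patient, in T0 SD units: 1 + k² - 2ρk.
- Residual variance after adjustment: k²(1 - ρ²).
- Small-sample cost of one covariate: f = 1 + 1/(2n - 4) = 1 + 1/76 = 1.013 at n = 40 per arm.
- Variance ratio = f × k²(1 - ρ²) / (1 + k² - 2ρk). At k = 1 this is f × (1 + ρ)/2.

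| ρ (k = 1, 40 per arm) | Variance ratio | 95% CI half-width, change score | 95% CI half-width, adjusted |
|---|---|---|---|
| 0.3 | 1.013 × 0.65 = 0.66 | 0.53 SD | 0.43 SD |
| 0.5 | 1.013 × 0.75 = 0.76 | 0.45 SD | 0.39 SD |
| 0.7 | 1.013 × 0.85 = 0.86 | 0.35 SD | 0.32 SD |

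Simulation of 20,000 trials at each ρ (k = 1, 40 per arm) gave ratios of 0.66, 0.76 and 0.86.

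Sensitivity to unequal SDs at 40 per arm:
- Best case, k = 0.8 and ρ = 0.3: 1.013 × 0.5824/1.16 = 0.51.
- Worst case, k = 1.25 and ρ = 0.7: 1.013 × 0.7969/0.8125 = 0.99.

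At 24 per arm (the 60% retention floor, 0.6 × 40) the k = 1 ratios are 0.66, 0.77 and 0.87, and the worst case is 1.00. The gain shrinks as the slope ρk approaches 1. Nowhere in this range is there a material loss.

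**The case against.** **On (a).** The sentence in 10.4.1 is general. Its wording offers the two ratings as examples, so the rank tests remain usable for other ordinal items. The plan already contains the right analysis for the ratings: CIs for the feasibility measures, descriptive summaries and the 3.5 target. Table 2 lists patients and providers at different time points, and nothing says they will be pooled. All of this stands, and it makes the defect one of wording. It does not make the named tests executable or supply an appropriateness measure. A reader might infer that the ratings have no valid planned analysis; 10.4.1 and 10.4.2 show otherwise.

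**On (b).** The change-score t-test is unbiased under randomisation and already uses T0. Chance imbalance at T0 is reflected in its interval. Section 10.4.3 gives SD estimation as its main aim, and the correlation and SD ratio used above are assumptions under which the gain can all but vanish. This also stands, and it rules out any claim of bias. But the plan does prespecify the arm comparison, and the more precise version uses data already scheduled.

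**Stronger readings the documents do not support.**
- A reader might take "If our intervention is successful, we would expect to see significantly greater improvement over time in our effectiveness outcomes" as an effectiveness success criterion. No section makes it a decision rule. The Synopsis and Sections 3 and 4.2 disclaim formal effectiveness hypotheses, and Section 10.2 says feasibility outcomes will inform the future trial.
- A reader might infer a biased baseline, because Section 9.1 repeats key baseline sections when mPal is viewed more than 30 days after T0, which only the mPal arm can trigger. The same section defines the pre-intervention assessment as T0, so T0 is the readable default. The documents give nothing from which to size a shift.

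**Conclusion.** The point holds in two parts of different kinds.

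(a) is an inconsistency in the document and needs no assumptions. As scheduled, FIM and AIM cannot enter the rank-sum or signed-rank tests of 10.4.1, and the appropriateness ratings in 10.4.1 and 10.4.2 have no counterpart in Table 2.

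(b) is an available improvement, not an error. At an assumed correlation of 0.5 with equal SDs and 40 per arm, adjustment narrows the half-width from 0.45 to 0.39 SD. The saving in variance is about 34%, 24% and 14% at correlations of 0.3, 0.5 and 0.7, and falls to almost nothing at high correlation with a larger T2 SD.

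The primary enrollment endpoint is unaffected. Overall severity is minor to moderate.

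**What to change.** **Section 10.4.1.** Remove feasibility and acceptability from the rank-test sentences, and keep those tests for ordinal items measured at T0 and T2 in both arms. Report FIM and AIM means with 95% CIs against 3.5, separately for mPal patients (T1) and providers (T3).

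**Appropriateness.** Either give it a measure and time point in Table 2, or delete it from 10.4.1 and 10.4.2.

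**Section 10.4.3.** Replace the between-arm t-tests with a linear model of each T2 score on arm and the original pre-randomisation T0 score, not the re-administered sections. Report the adjusted difference with its 95% CI as exploratory, together with the T0 and T2 SDs and the T0-T2 correlation for planning. Change scores may stay for the planned correlations with referrals.

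**Optional clarifications.** State which knowledge score is modelled, since the Table 2 row reads "10 items; assesses self-reported PC knowledge and PC perceptions. PACKS" after naming HINTS PC. Soften the sentence that links success to significant improvement.

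**Cost.** Wording in 10.4.1, 10.4.2 and 10.4.3, and one covariate. No new data collection is needed unless the sponsor chooses to add an appropriateness measure.
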